## 1.5 Correlative Studies

The correlative studies will explore the mechanisms of possible immune enhancement by SABR. Activation of each arm of the immune response will be evaluated separately utilizing different assays. The humoral response will be evaluated using ELISA to measure the titer of tumor-specific antibodies generated by SABR and HD IL-2 against tumor tissue collected from the respective patients and established human renal cancer cell line Caki-2 (clear cell) and ACHIN (adenocarcinoma). An overall increase in tumor antigen-specific antibody will be measured using immunoblotting with patient sera as a source of primary antibody.

Enhancements of increased cytotoxicity to renal cancer cells can be measured by cytotoxicity assays. Antibody-dependent cell-mediated cytotoxicity (ADCC) measures the cell-killing ability of certain lymphocytes that require the target cell to be marked by an antibody and thus measures the humeral response [28]. On the other hand, lymphocyte-mediated cytotoxicity assay will measure the formation of tumor-specific CTLs among the lymphocytes collected from patients with the controls being lymphocytes collected from the same patients before SABR and before HD IL-2. Since it is not practical or feasible to obtain sufficient quantities of tumor cells from each patients to assess a quantitative cytotoxicity by these assays, established allogenic human human renal cancer cell line Caki-2 and ACHIN will be used for this purpose. It is a generally accepted principle of tumor immunology that there will be many common tumor antigens between different patient tumors of same site origin, and therefore tumor cell lines as well [28]. In fact, the tumor antigens (PSA, CEA, CA 19-9 etc.) that are in clinical practice are reported to be present in a significant portions of patients of the respective tumor site. This concept of commonality of tumor antigens between allogenic tumor cell lines and patients is put into clinical practice by the GVAX anti-tumor vaccine which is currently in early phase clinical trials for pancreatic, melanoma and renal cancer [62, 63]. GVAX consists of multiple human tumor cell lines of the respective site, that is modified to express GM-CSF, and killed with radiation prior to injection in patients. The presence of common tumor antigens in the cell lines and patient's tumors, leads to induction of an immune response. The LNCaP and PC-3 cell lines has been shown to express many of the common renal cancer antigens, and therefore, is an appropriate surrogate to be used instead of patient's own cells and has been used in similar in vitro cytotoxicity assays [64-68].

Cytokines are hormonal messengers responsible for most of the effects in the immune system such as activation of innate versus adaptive immune response, cellular versus humeral immune response [69, 70]. For example, an increased level of IL-2 and IFN- $\gamma$  suggests activation of Th1 cells leading to activation of macrophages and suggests a cell-mediated adaptive immune response whereas IL-4 and IL-5 may indicate Th2 activation and induction of humoral immunity [28, 70]. An increase in IL-17 may suggest activation of autoimmune responses [71]. Therefore, measurements of serum cytokine levels have generally been used previously in clinical trials as surrogates to assess specific activation of immune pathways [72, 73]. Serum cytokines from this clinical trial before and after SABR will be measured using an extensive array of cytokines to explore the specific immune pathways that are initiated by SABR. The planned array of cytokines will measure levels of the following cytokines before and after treatment for each patients: Th1/Th2/Th17 cytokines: IFN- $\gamma$ , IL-1 $\beta$ , IL-2, IL-4, IL-5, IL-8, IL-10, IL-12p70, IL-13, IL-17 TNF- $\alpha$ ; pro-inflammatory cytokines: GM-CSF, IFN- $\gamma$ , IL-1 $\beta$ , IL-2, IL-6, IL-8, IL-10, IL-12p70, TNF- $\alpha$ ; Chemokines: Eotaxin, MIP-1 $\beta$ , TARC, IP-10, IL-8, MCP-1, MCP-4, KC, and others including IL-6, IL-12, TGF- $\beta$  and HMGB1.

Many surrogate markers for activated and proliferating lymphocytes have been described. Some of these markers include CD25, CD71, CD45RO, CD107a, CD54, CD69, Ki67 and ICOS/CD278 [74-77]. These markers are easily measured with antibodies specific for the markers that are tagged with a fluorophore utilizing FACS analysis. Also using FACS, activation markers on other immune cells such as CD80 and CD 86 on DCs, and inhibitory markers on monocytes such as PD-1 can be measured as surrogates of immune activation or inhibition. These measurements from PBMCs collected from patients before and after treatment will give us further information

regarding the intensity of the immune response. Additionally, PD-L1, the ligand of PD-1, often expressed in tumor cells, can be quantified from patient pre-treatment tumor biopsy.

The relative levels of different monocyte subpopulations in the tumor biopsy sample after treatment as well as in the peripheral circulation often dictate the overall outcome of an immune response, and has been reported in previous immunotherapy trials [61]. Exploration of possible mechanisms of treatment failure can be explored from this analysis as well. Therefore the following subpopulation of cells will be quantified in patient PBMCs (and in tumor biopsy samples where applicable) collected before and after treatment utilizing some of the listed markers specific for those cells:

Immune Cells	Markers		
Lymphocytes			
Cytotoxic T Lympocyte (CTL)	CD3, CD8		
NK	CD3-, CD8, CD16, CD56, CD11b		
NKT	CD3, CD16, CD1d		
Helper T Cells	CD3, CD4		
Th1	IL-18 receptor α, CXCR3, T cell Ig		
	domain, TIM-3, T-bet		
Th2	T1/ST2, TIM-1, TIM-2, GATA-3		
Th17	Unknown, differentiated by IL-17		
	production, ROR-γT		
Treg	CD4+CD25+FoxP3+		
Memory T Cells	CD45RO		
Тсм	CD4/CD8, CD62L, CCR7		
Тем	CD4/CD8, CCR7-, CD45RA-, CD27		
B Cells	CD19, mlg, FcR, CR, CD3-, HLA-DR		
MDSC	CD14+, CD11b, CD33, CD 15, CD4,		
	CD8-, HLA-DR-/low		
Neutrophils	FcR, CR-,CD3-, HLA-DR-, GR-1 +high ,		
	CD11b, Ly6G		
Macrophages	FcR, CR, HLA-DR, GR-1 +mid		
DC			
Myeloid DC-1	CD11c, TLR2,TLR4		
Myeloid DC-2	CD 141, TLR2,TLR4		
Plasacytoid DC	CD303, TLR7, TLR9		

Table 1: PBMC subpopulations and their markers.

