- **9.2.4** Chromium Release Cytotoxicity Assays: For cell-mediated cytotoxicity analysis, A 50 μl sample of Cr-labeled target cells (Caki-2 and ACHIN human renal cancer cells) is mixed with 100μl of effector cells (patient PBMC) at various target to effector ratio (E:T ratios). After centrifugation at 100 X G, the cells are incubated for 2 hr at 37°C. The radioactivity of culture supernatant is measured using a gamma counter and percentage of cytotoxicity is calculated. For antibody-dependent cytotoxicity analysis this procedure will be performed with patient's plasma instead of PBMC and the percentage of cytotoxicity is calculated in similar manner. An alternate and non-radioactive labeling method utilizes GAPDH enzyme release from lysed cells called Bioluminescence Non Radioactive Cytotoxicity Assay (aCella-TOX, T Cell Technology, INC) [109, 110].
- **9.2.5** Flow cytometric analysis (FACS): For FACS analysis of cell-surface molecules, the cell samples are stained with fluorescent dye conjugated monoclonal antibodies against the selected markers on ice followed by fixation with 4% paraformaldahyde. Data are acquired on a LSRII (BD Biosciences) and analyzed using FACSDiva software (BD Biosciences). The PBMC of each patient before and after treatment will be analyzed to identify the relative sub-population of CTLs,

regulatory T-Cells, effector memory T cells, MDSCs, neutrophils and NK cells utilizing appropriate cell surface markers (see section 1.5).

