- 9.2.6 **Immunohistochemical staining (IHC):** Standard immunohistochemistry staining procedure for will be performed using the Benchmark XT automated stainer (Ventana) for both antibodies. Briefly, formalin-fixed, paraffin-embedded tissue sections will be cut at 3-4 micron and air-dried overnight. The sections will be deparaffinized, rehydrated, and subjected to heat-induced epitope retrieval. Sections will then be incubated with appropriate primary antibody. For signal detection, ultraView universal detection system (Ventana) will be used. The slides will be developed using 3-3'-diaminobenzidine chromogen and counterstained with hematoxylin. Appropriate positive and negative controls will be utilized for each run of immunostains. The evaluation of the immunostaining will be carried out by a genitourinary pathologist without knowledge of any clinicopathologic data. Only nuclear reactivity will be considered positive. An H score will be assigned as the product of average intensity of staining (0 for negative, 1 for weakly positive, 2 for moderately positive, and 3 for strongly positive) and extent of immunoexpression (0-100% percentage of cells staining). In addition, Dualantibody ISH will be performed to identify and analyze TILs, CTL (CD3+,CD8+), Tregs (CD4+FoxP3), DC (CD11c), NK/T (CD3+, CD1d), neutrophils (CD11b, Ly6G} and MDSC (CD14+,CD11b) in the tumor tissue before and after treatment, when available (see section 1.5).

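### The staining methods for blood Tregs (no FoxP3 step) and tumor MDSCs (no HLA-DR) do not measure the cells that Table 1 defines; the effect is confined to the exploratory biomarker objective

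*Combined protocol and SAP*

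**What the plan says.** Section 1.5 lists the immune cell subsets to be counted and their markers in Table 1. The Treg row is "CD4+CD25+FoxP3" positive. The MDSC row names CD14, CD11b, CD33 and other markers, and ends with HLA-DR negative or low. The macrophage row begins "FcR, CR, HLA-DR, GR-1", so it carries HLA-DR as a positive marker. The sentence introducing the table says subsets will be quantified in samples "collected before and after treatment utilizing some of the listed markers specific for those cells".

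Section 9.2.5 gives the blood method: "For FACS analysis of cell-surface molecules, the cell samples are stained with fluorescent dye conjugated monoclonal antibodies", followed by fixation. It assigns several subsets, regulatory T cells among them, to surface markers, ending the list with "MDSCs, neutrophils and NK cells utilizing appropriate cell surface markers" and a pointer back to section 1.5.

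Section 9.2.6 gives the tissue panel. Tregs there are CD4 with FoxP3. The last entry is "MDSC (CD14+,CD11b) in the tumor tissue before and after treatment, when available".

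Section 1.5 also names markers of activated and proliferating lymphocytes: "Some of these markers include CD25, CD71, CD45RO, CD107a, CD54, CD69, Ki67 and ICOS/CD278".

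**The concern.** A subset count can be interpreted only if the stain separates that cell from its neighbours. FoxP3 is what distinguishes Tregs from other CD4+CD25+ cells in Table 1. HLA-DR is what the table shows separating MDSCs from macrophages. Each of these markers is missing from one of the two methods.

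The timing adds to the Treg problem. Section 1.3 describes IL-2 as driving T-cell activation and proliferation, and section 5.2.6 schedules a blood draw on the last day of the second IL-2 cycle. If blood Tregs were read from CD4 and CD25, a rise in CD25 at that draw could be reported both as activation and as more Tregs.

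MDSCs belong to the stated mechanism: sections 1.2 and 1.4.1 (immunologic rationale) associate response with a fall in them. Section 1.4.1 also expects more antigen-presenting cells in all tumor sites. A tumor count that mixes HLA-DR-positive myeloid cells with MDSCs would be hard to set against that expectation.

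The open wording of section 1.5 also lets the markers for a subset be chosen after outcomes are known.

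**Working it through.** No arithmetic applies, because the plan states no figure that depends on these definitions. The check compares the Table 1 definition with the method for each cell type in each kind of sample. Two facts come from general immunology and not from the documents: FoxP3 is intracellular, and HLA-DR is a surface molecule.

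| Subset and sample | Table 1 requires | Method as written | Can the definition be met? |
|---|---|---|---|
| Treg, blood (9.2.5) | CD4, CD25, FoxP3 | Surface markers, stain then fix | No: FoxP3 cannot be reached |
| Treg, tissue (9.2.6) | CD4, CD25, FoxP3 | CD4 with FoxP3 | FoxP3 is kept, so not affected |
| MDSC, blood (9.2.5) | CD14, CD11b and others, HLA-DR negative or low | Surface markers, pointer to 1.5 | Yes: HLA-DR can be stained |
| MDSC, tissue (9.2.6) | CD14, CD11b and others, HLA-DR negative or low | CD14 and CD11b only | No: HLA-DR is dropped |

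**Blood Tregs.** The procedure is "stained with fluorescent dye conjugated monoclonal antibodies against the selected markers on ice followed by fixation with 4% paraformaldahyde". Antibody is applied before fixation, and no permeabilisation step is described, so an antibody to FoxP3 would not reach its target. The surface markers left in the Treg row are CD4 and CD25, and CD25 is on the protocol's own list of activation markers.

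**Tumor MDSCs.** Section 9.1.2.1 sends the pre-treatment cores to paraffin blocks and tumor lysates. Only the elective 8-week cores are prepared for flow cytometry (9.1.2.2). Flow therefore cannot supply a before-and-after comparison in tumor, and any such comparison rests on the CD14 and CD11b stain in 9.2.6.

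**Reach.** The subsets serve objective 2.3.1, which is exploratory. The immune-response endpoint (2.4.4) uses ELISpot, T-cell proliferation and ELISA. Section 11.3 plans repeated-measures analyses for ELISpot and the proliferation index and none for flow or tissue subsets. The response-rate endpoint and the two-stage sample size do not use these counts.

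**The case against.** The strongest reply is that this is a loose summary of laboratory methods and not an exclusion of FoxP3. Section 9.2.5 points back to section 1.5, where FoxP3 is in the Treg row, and no text says that blood Tregs will be counted as CD4+CD25+ alone. Section 1.5 also treats Ki67, another intracellular marker, as measurable by flow cytometry, so the laboratory may well intend intracellular staining. Much of this stands. It makes the point a contradiction between sections, and it means activated cells *may* be counted as Tregs, not that they will be. It does not supply the missing step: someone following 9.2.5 would not obtain FoxP3.

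On tissue, Table 1 does not list CD14 or CD11b for macrophages, so the overlap with macrophages rests on general immunology. The documents show only that the distinguishing marker is absent. The post-treatment biopsy is elective, so few patients may have paired tissue. Both remarks are fair and limit the weight of the point.

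A reader might infer that Tregs and MDSCs cannot be identified anywhere in this trial. The table above shows otherwise: tissue Tregs keep FoxP3, and blood MDSCs can be defined with HLA-DR. A reader might also infer that the blood Treg error undermines the stated mechanism. Tregs do not appear in the rationale of sections 1.2 to 1.4; MDSCs do, and their predicted fall can still be examined in blood.

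**Conclusion.** The point holds for two of four combinations: blood Tregs and tumor MDSCs. As written, neither method delivers the definition in Table 1, and the phrase about using some of the markers does not close the gap.

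It is tempting to go further and say that the counts would be inflated several-fold, or that the direction of a treatment effect would reverse. The documents do not support either statement. They give no Treg frequency, no expected rise in CD25 and no share of HLA-DR-positive cells among tumor CD14+CD11b cells, so any multiple would only restate assumed inputs.

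The consequence is limited to interpreting two exploratory readouts under objective 2.3.1. The primary endpoint, sample size, stage-one decision and immune-response endpoint are untouched. It is worth correcting because the correction is cheap and the samples are stored. The conclusion rests on the two general immunology facts stated above and on 9.2.5 and 9.2.6 being followed as written.

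**What to change.** - **9.2.5:** add a fixation and permeabilisation step with intracellular FoxP3 for the Treg tube, and count blood Tregs only as CD4+CD25+FoxP3+.
- **9.2.6:** relabel the tissue stain *CD14+CD11b+ myeloid cells*, or add HLA-DR to it. If it is only relabelled, report MDSCs solely from flow cytometry with HLA-DR negative or low.
- **1.5:** state that FoxP3 for Tregs and HLA-DR negative or low for MDSCs are mandatory. The other Table 1 rows, some of which list alternatives or give the marker as unknown, need not change for this purpose.

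**Cost.** The change needs protocol and laboratory-manual wording, one extra antibody tube, and some stored blood cells per sample. It adds no patient procedure, since section 9.1.1 already freezes cells in 5 aliquots. Cell numbers may be limiting at the draw one hour after the first SABR fraction, which takes 20 ml in EDTA against about 100 ml at the other times, one fifth of the volume (20/100). The same cells also feed the ELISpot, proliferation and cytotoxicity assays, so the laboratory should set a priority order for that draw. If the tissue stain is only relabelled, the trial has no before-and-after tumor MDSC readout. Keeping one means adding HLA-DR as a third marker to a panel described as dual-antibody.

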## 1.6 Health-related Quality of Life (HRQOL) and Economic Analysis

In the United States, total national health expenditures (NHE) increased from \$7.14 billion in 1990 to \$2.23 trillion in 2007, which represents an average annual growth rate of 7.0%. In contrast, over the same period, U.S. gross domestic product (GDP) increased from \$5.8 trillion in 1990 to \$13.8 trillion, or average 5.2% annual growth rate. Given that national health expenditures have grown faster than GDP, the share of GDP devoted to health expenditures has increased from 12.3% in 1990 to 16.2% in 2007[78]. Moreover, national health expenditure growth is expected to continue to outpace income growth, with total NHE reaching \$4.35 trillion by 2018, accounting for 20.3% of GDP (CMS 2009). There is growing concern that these trends in health expenditures are not sustainable. For the Medicare program, current estimates of the present value of total unfunded liabilities through the year 2083 (the present value of the difference between projected future Medicare expenditures and Medicare revenues over the next 75 years under current Medicare policy) total \$89 trillion, with Medicare's Hospital Insurance ("Part A") trust fund projected to be depleted by 2017[79].

Prior studies have estimated that about half of the recent growth in health expenditures is attributable to advances in various forms of health technology, including new pharmaceutical products, surgical procedures, imaging modalities, and new biomarkers[79]. While almost all of these new technologies offer some potential to improve clinical outcomes, they also more often than not add to health expenditures. Within the context of unsustainable trends in health expenditures, a key policy question relates to whether the extent of improvement in outcomes associated with the use of a new technology is attained at a "reasonable" additional cost, compared to existing technology. Indeed, the value offered by new technologies is being subjected to increasing scrutiny by reimbursement authorities in many health systems worldwide. For example, in the United Kingdom, the National Health Service bases payment policy decisions for new technologies on recommendations from the National Institute for Health and Clinical Excellence (NICE), which in turn are substantially influenced by cost-effectiveness analysis yielding an estimated additional "cost per quality-adjusted life-year (QALY) gained" via use of the new technology. Currently, NICE usually considers technologies offering improved outcomes at a cost less than £20,000 to £30,000 per QALY gained (about \$33,000 - \$50,000) acceptable, though exceptions are common[80].

There was no quality-of-life data reported in the French trial evaluating IL-2, INF-alpha, or both [39]. However, in an abstract evaluating the QoL of patients taking different regimens of IL-2 there was no difference found. [81] In a phase 3 study evaluating high-dose IL-2 versus subcutaneous IL-2 and INF-alpha in patients with mRCC, the authors comment that there was no difference in quality of life assessments for patients treated with high-dose arm, no specific measures, utilities, or values were published [35]. Several recent studies have evaluated health-related quality of life (HRQoL) for biologics and targeted treatment for mRCC. In the Sunitinib versus INF-alpha trial health-related quality of life was superior in the sunitinib group as assessed by the FKSI-15, FACT-G, and EQ-5D [82],[83]. In a review article regarding quality-of-life measures recent renal cell cancer protocols by Cella at al., it is clear that quality-of-life measures are increasingly being utilized within the clinical trial setting to assess guality adjusted life year expectancy [84]. Two recent trials evaluating health-related quality of life for sorafenib utilizing the FACT-FKSI, FACT-G, and EQ-5D indicated that Strachan of treatment resulted in improvements in individual items related to registry function and quality of life compared with placebo [85]. Additionally, European trials evaluating temsirolimus in a phase 3 setting versus INF-alpha or both, showed quality adjusted survival favoring patient who received temsirolimus [86]. In a group of heavily pretreated metastatic renal cell cancer patients enrolled on a phase 3 trial comparing everolimus versus placebo, guality of life as measured by EORTC QLQ C30 and FKSI-DRS showed no changes between the two treatment groups showing stable quality-of-life as compared to placebo. [87] Additionally, there are ongoing studies evaluating axitinib as well.

Due to the high cost of these new therapeutic agents several cost-effectiveness studies have evaluated the cost per quality adjusted life year of first-line therapeutic options of metastatic renal cell carcinoma. In an economic analysis of sunitinib versus INF-alpha and IL-2, Sunitinib was shown to be a cost-effective alternative to INFA-alpha and IL-2 from a US societal perspective [88]. An economic analysis from the Chinese perspective was undertaken evaluating INF-alpha, IL-2, INF-alpha plus IL-2, sunitinib, and bevacizumab plus INF-alpha, showed thatsunitinib was cost effective when the willingness to pay threshold was over \$16,000 which would be appropriate for several developed regions within China [89]. Given the rising costs associated with the biologic and targeted therapies for metastatic renal cell carcinoma the cost implications of of this protocol warrant study.

Therefore, we propose to evaluate patients' health related quality of life (HR-QoL) and health state utilities in order to evaluate the economical consequence of using the two treatments proposed in this study and their impact on quality adjusted survival. Based on the primary hypothesis of this study that response rates will be improved with the combination of SABR and HD-IL2, we further hypothesize that the addition of SBRT will increase the durability of response or lengthen the time

to progression thus increasing the cost effectiveness of the combined therapies. Thus, we hypothesize that the added treatment of SBRT while adding modestly to the total cost of the combined therapies may be cost saving over the patient's entire treatment course compared to HD-IL2 alone, making the combination a very attractive treatment for mRCC patients. Additionally, we hypothesize that combination of SBRT and HD-IL2 will increase the quality-adjusted life-years for mRCC cancer patients (compared to the prior reported chemotherapeutic, biologic, and targeted options for mRCC) at a reasonable incremental cost, as defined by generally accepted cost-effectiveness thresholds. The sample size would be prohibitively large should these secondary endpoints be analyzed beyond simple descriptive statistical purposes.

